#### 4.12.2 Dysgeusia

Loss of taste (dysgeusia) is an on-target adverse event known to occur with porcupine inhibition. A taste assessment questionnaire will be performed at screening and at each study visit when patient reports dysgeusia.

A bar-chart will present the worst answers to the main questions after screening and a separate one illustrating the worst answers on the way the taste is altered. In the event a patient answering in both directions of 'more sensitive' or 'loss' then loss will be considered worse. A by-patient listing will also be provided.

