4.4.1.6 RXC004 1 mg Monotherapy Dose

Patients who participate in Cohort 2 of Module 2 will receive RXC004 1.0 mg orally QD. The purpose of this cohort is to further characterise the dose-response relationships for activity and safety and to support the optimal dosage(s) for future clinical development.

In the Phase 1 study, the dosing cohorts were small (see Section 4.4.1.1) and patients were not selected for having Wnt ligand-dependent tumours. The median RXC004 exposure was short (approximately 7 weeks); thus, the AEs described in Section 4.4.1.1 were generally observed during the first 2 treatment cycles. Of the observed AEs, only dysgeusia, a known on-target toxicity of Wnt pathway inhibitors, was observed to be dose-related and 4 out of 6 patients in the 2 mg cohort reported dysgeusia within the first 2 treatment cycles. Cohort 2 of Module 2 will explore whether the lower dose of 1 mg has the potential to deliver clinical anti-tumour activity in patients with BTC, a Wnt ligand-dependent tumour, and whether this lower dose has the potential to reduce incidence of treatment related toxicities such as dysgeusia. The 1.5 mg dose was not selected for this purpose because the PK profiles of the 1.5 mg dose and 2 mg dose show considerable overlap.

Initiation of this lower dose cohort will depend on emerging data from the RXC004 2 mg dose cohort. Should the 2 mg dose fail to show any anti-tumour activity in Cohort 1 that warrants further investigation (as per Section 11.9.1), then this lower dose cohort (Cohort 2 of Module 2) will not open unless the SMC consider that the tolerability of the 2 mg QD dose has compromised its ability to show efficacy.

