8.3.12 Dysgeusia

Loss of taste (dysgeusia) is an on-target adverse event known to occur with porcupine inhibition. According to CTCAEv5, there are only two grades of dysgeusia:

Grade 1 - Altered taste but no change in diet.

Grade 2 - Altered taste with change in diet (e.g. oral supplements); noxious or unpleasant taste; loss of taste.

As dysgeusia is poorly characterised by CTCAE grade alone, site research personnel will complete a taste assessment (consisting of a specific set of questions and an oral examination) at screening for each patient enrolled, and for any patient who reports dysgeusia in response to the open question from the study site staff: ‘Have you had any health problems since the previous visit/you were last asked?’. In such cases, the assessment will be performed at each visit until the adverse event has resolved. The information will be recorded and analysed as part of the overall safety objective of the study.

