#### **4.2.9 Analysis Conventions**

Continuous data will be summarized in terms of the mean, standard deviation, median, minimum, maximum and number of observations, unless otherwise stated.

The minimum and maximum will be reported to the same number of decimal places as the raw data recorded in the database. The mean, median, will be reported to one more decimal place than the raw data recorded in the database. The standard deviation will be reported to two more decimal places than the raw data recorded in the database. In general, the maximum number of decimal places reported shall be four for any summary statistic.

Categorical data will be summarized in terms of the number of patients providing data at the relevant time point (n), frequency counts and percentages. Any planned collapsing of categories will be detailed in the SAP text and the data displays.

Percentages will be presented to one decimal place. Percentages will not be presented for zero counts. Percentages will be calculated using n as the denominator.

Changes from baseline in categorical data will be summarized using shift tables where appropriate.

Confidence intervals will be presented to one more decimal place than the raw data.

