### 4.12 Safety Evaluation

Safety summaries and analyses will be based on the FAS as defined in Section 4.5.

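### The taste-questionnaire chart in SAP 4.12.2 does not set the on-study answer against the screening answer, and its denominator is left open

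*SAP*

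**What the plan says.** Protocol section 3 names assessment of dysgeusia among the safety endpoints. Protocol 8.3.12 explains that CTCAE, with only two dysgeusia grades, describes the event poorly. It therefore requires a taste assessment "at screening for each patient enrolled, and for any patient who reports dysgeusia in response to the open question" about health problems. SAP 4.12.2 gives the same timing: "A taste assessment questionnaire will be performed at screening and at each study visit when patient reports dysgeusia".

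SAP 4.12.2 plans three outputs:

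- a first chart: "A bar-chart will present the worst answers to the main questions after screening";
- a second chart: "a separate one illustrating the worst answers on the way the taste is altered", with no time span written;
- a listing: "A by-patient listing will also be provided".

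A patient who answers in both directions is scored as loss. SAP 4.12.1 adds a listing of the questionnaire data, and a categorical summary only if there are enough data to make one worthwhile.

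Two general rules bear on the denominator. SAP 4.12 states: "Safety summaries and analyses will be based on the FAS as defined in Section 4.5". SAP 4.2.9 defines n for categorical data as the patients with data at the time point and adds: "Percentages will be calculated using n as the denominator".

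**The concern.** The questionnaire exists to add what the CTCAE grade cannot give, and its screening assessment supplies a baseline for every patient. A chart of post-screening answers alone leaves that baseline unused. Some patients may enter with altered taste: all have had prior systemic therapy, and core exclusion criterion 6 (Protocol 5.4) bars only residual effects above Grade 1. Grade 1 dysgeusia is altered taste without a change in diet. If such a patient reports dysgeusia on study, the chart shows the worst answer with nothing to say whether it differs from screening.

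The second issue is the base on which the bars stand. After screening, only patients who report dysgeusia complete the questionnaire. A percentage of those patients and a percentage of all treated patients are different quantities, and the SAP does not say which is meant.

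This matters because Protocol 4.4.1.1 singles out dysgeusia as the one event that looked dose-related, and the 1 mg cohort of Module 2 is meant to explore "whether this lower dose has the potential to reduce incidence of treatment related toxicities such as dysgeusia". A percentage taken among reporters can look the same at two doses even when the share of treated patients affected differs.

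**Working it through.** The plan states no figure for this display. The check is a comparison of sections followed by simple arithmetic on the Phase 1 rates.

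**1. Handling of baseline elsewhere in the SAP.** Baseline-to-worst shift tables are planned for laboratory grades (4.12.3), blood pressure (4.12.4.1), QTcF (4.12.4.3), Karnofsky status (4.12.4.4) and ECOG status (4.12.4.5). SAP 4.2.9 allows shift tables for categorical data where suitable. Section 4.12.2 asks for none, although the questionnaire is categorical and every patient has a screening value.

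**2. Reporting rates.** Protocol Table 3 gives Phase 1 monotherapy dysgeusia as 0/4 at 0.5 mg, 0/3 at 1 mg, 2/7 at 1.5 mg and 4/6 at 2 mg.

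- Up to 2 mg: (0+0+2+4)/(4+3+7+6) = 6/20 = 30%, which agrees with Protocol 2.3.1.2.
- At 2 mg: 4/6 = 66.7%, which agrees with Protocol 4.4.1.6.

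**3. Effect of the denominator.** If a share r of the FAS reports dysgeusia, the percentage among reporters equals the FAS percentage divided by r.

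- r = 30%: 1/0.30 = 3.3 times.
- r = 66.7%: 1/0.667 = 1.5 times.

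For example, an answer given by half of reporters (assumed) is 0.50 × 0.30 = 15% or 0.50 × 0.667 = 33% of the FAS.

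**4. Effect on a dose comparison.** Suppose half of reporters answer loss at both 1.5 mg and 2 mg (assumed). Both bars read 50%. The shares of treated patients are 0.50 × 2/7 = 14% and 0.50 × 4/6 = 33%.

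**5. Unchanged answers among reporters.** Let b be the share of the FAS with altered taste at screening that does not change and is reported on study. The documents give no value, so b = 5% to 10% is an assumption. If these patients are already counted in r, their share of reporters is b/r. If they come on top of r, it is b/(r+b). The second form is the more natural one, because the Phase 1 counts are of treatment-emergent events.

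| r | b | b/r | b/(r+b) |
|---|---|---|---|
| 30% | 5% | 5/30 = 17% | 5/35 = 14% |
| 30% | 10% | 10/30 = 33% | 10/40 = 25% |
| 66.7% | 5% | 5/66.7 = 7.5% | 5/71.7 = 7% |
| 66.7% | 10% | 10/66.7 = 15% | 10/76.7 = 13% |

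Under these assumptions, between about 7% and 33% of the answers charted would show no change from screening.

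**The case against.** The strongest defence is that the charts are not meant to measure incidence. How often dysgeusia occurs comes from the treatment-emergent adverse event tables (SAP 4.12.1). Those are on the FAS and count a pre-existing event only if it worsens. The questionnaire describes the character of the event, and the listings show each patient's data. That is right as far as incidence goes, and it keeps the point small. It does not supply a summary of change in the questionnaire answers, which is what the instrument adds to the CTCAE grade; the one further summary is conditional.

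A reader might infer more than the documents support:

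- *That the charts present pre-existing taste change as an RXC004 effect.* The SAP attaches no causal label. A pre-existing change enters only if the patient reports dysgeusia in answer to a question about the interval since the last contact. The limit to answers after screening is written for the first chart only.
- *That the FAS is not the denominator.* SAP 4.12 points to the FAS and SAP 4.2.9 to patients with data. The bars may also be counts. The denominator is unresolved, not fixed on reporters.
- *That the charts and the adverse event tables must conflict.* They answer different questions and could differ without either being wrong.
- *That up to half of the altered answers are not new.* That takes an assumed 15% prevalence over the lowest reporting rate (15/30 = 50%). At 2 mg the same assumption gives 15/66.7 = 22%, and neither figure rests on data in the documents.
- *That lost taste at entry is a common route.* Loss is Grade 2, so exclusion criterion 6 would bar it if left over from prior anti-cancer therapy. The concern is mainly altered taste.

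The wording of the questions is not in the documents, so whether a screening comparison is informative must be confirmed question by question. Scoring loss as the worse answer is a pre-specified choice and is acceptable.

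**Conclusion.** The point holds as a minor gap in a descriptive safety output. No firm summary in the SAP uses the screening taste answer, so the first chart cannot separate altered taste already present at entry, and reported again on study, from change that began on treatment. The denominator is unresolved between two SAP rules. If percentages on reporters were shown, they would be about 1.5 to 3.3 times the FAS percentage. That range assumes that reporting in this study resembles the small Phase 1 groups (4/6 and 6/20) and is illustrative only. How many reporters would show no change from screening cannot be known from the documents. The primary endpoint, the decision rules and the adverse event incidence tables are unaffected.

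**What to change.** In SAP 4.12.2:

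- For each main question, show the screening answer against the worst post-screening answer, as a shift table or paired bars, in line with the shift displays already planned for other safety measures.
- State the denominator as all FAS patients in the module or, for Module 2, the dose cohort. Add a category for patients who reported no dysgeusia and so were not assessed after screening.
- Say whether the second chart is also restricted to answers after screening.
- Keep the rule that scores loss as worse.

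The cost is a few lines of SAP wording and one re-specified display. The data are already collected, so no protocol or case report form change is needed.

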#### 4.12.3 Clinical Laboratory Evaluation

Blood samples for determination of clinical chemistry and haematology will be taken at the visits indicated in the SoA (see protocol). Additional safety samples may be collected if clinically indicated at the discretion of the Investigator. The date, time of collection and results (values, units and reference ranges) will be recorded on the eCRF.

The clinical chemistry and haematology will be performed at a local laboratory at or near to the investigator site. Sample tubes and sample sizes may vary depending on laboratory method used and routine practice at the site.

In case of BLQ values (eg "<5", "<100") for some assessments, the following rule will be considered:

- If less than 50% of the assessments (across patients) are BLQ such as "<XXX", then "XXX/2" will be considered for summaries.
- If 50% or more than 50% of assessments (across patients) are BLQ such as "<XXX" then "0" will be considered for summaries.

The following laboratory variables will be measured:

- Haematology (whole blood): Haemoglobin (Hb), Lymphocytes (absolute count and %), Neutrophils (absolute count and %), Platelet count, Total white cell count.
- Clinical Chemistry (serum or plasma): Albumin, Alanine transaminase (ALT), Alkaline phosphatase (ALP), Amylase, Aspartate transaminase (AST), Calcium, Calcium corrected, Creatinine, CRP, Glucose, Lactate dehydrogenase (LDH), Lipase, Magnesium, Phosphate, Potassium, Sodium, Total bilirubin, Urea.

The original lab test units will be converted using the International System of Units (SI).

Laboratory test with numerical grading criteria in the NCI CTCAE version 5.0 will be graded accordingly. Grade 0 will be assigned for all non-missing values not graded as 1 or higher. For laboratory tests where grades are not defined by NCI CTCAE version 5.0 results will be classified as low, normal or high based on laboratory normal ranges.

The following summaries will be provided for all parameters:

- Summary statistics of values and absolute change from baseline by visit (as per SoA)
- Shift tables will be provided for all parameters to compare a patient's baseline laboratory grade relative to worst post-baseline grade (Low and/or High abnormal direction will be considered for each parameter).

By-patient listing will be provided for all patient in FAS by visit, including values, changes from baseline, grade and reference range. All values outside the clinical reference ranges will also be flagged in the data listings. The abnormal values will be flagged with 'L' for values below the lower limit of the clinical reference range and 'H' for values above the upper limit of the clinical reference range. In addition, box plots presenting the results per visit will be presented for each lab parameter.

eDISH plots will also be produced to assess the liver toxicity.

#### 4.12.4 Vital Signs, Physical Examinations and Other Observations Related to Safety

##### 4.12.4.1 Vital Signs

The following vital signs will be recorded at baseline and post-baseline visit:

- Weight (kg)
- Temperature (°C or °F)
- Systolic blood pressure (in mmHg)
- Diastolic blood pressure (in mmHg)
- Pulse rate (beats/minute)
- Respiratory rate (breaths per minute)
- BMI
- O2 Saturation

A shift table from baseline systolic blood pressure and diastolic blood to worst on-treatment results will be presented. The normal/abnormal classification will be made using the criteria defined in table below:

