### 4.2.2 Visit Windowing

By visit summaries will be made considering the windows as below. The visit windowing is assessed relative to C1D1 date (not C0D1 due to delays between C0D1 and C1D1).

C0D1	C0D1
C1D1	(C1D1 - Day 8)
Day 15	(Day 9 - day 18)
Day 22	(Day 19 - Day 32)
Day 43	(Day 33 - Day 53)
Day 64	(Day 54 - Day 74)
Day 85	(Day 75 - Day 95)
Day 106	(Day 96 - Day 116)
Day 127	(Day 117 - Day 137)
Day 148	(Day 138 - Day 158)
Day 169	(Day 159 - Day 179)
Day 190	(Day 180 - Day 200)
Day 211	(Day 201 - Day 221)
Day 232	(Day 222 - Day 242)
Day 253	(Day 243 - Day 263)
Day 274	(Day 264 - Day 284)
Day 295	(Day 285 - Day 305)
Day 316	(Day 306 - Day 326)
Day 337	(Day 327 - Day 347)
Day 358	(Day 348 - Day 368)

The following visits will not be remapped: Screening, IP Discontinuation, 30/90 Day Follow-up, Survival Follow-up.

In case several visits occur into the same windows the following rule is to be applied:

- For by-visit table, we will consider the mean of available assessments.
- For Shift table, we will consider either Minimum or Maximum available value depending on the direction.

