**Table 2 – Vital Sign Criteria for Abnormalities**

Vital Sign Criteria for Abnormalities	Criteria for Abnormalities (any of the following situation)
Systolic blood pressure	value < 80 mmHg value > 129 mmHg
Diastolic blood pressure	value < 60 mmHg value > 80 mmHg

Vital signs data and clinically relevant abnormalities in vital signs will also be listed.

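### The blood-pressure shift table pools low and high readings into one abnormal class and never defines 'worst', so it can hide a fall in diastolic pressure and show a fall in systolic pressure as improvement

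*SAP*

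**What the plan says.** SAP 4.12.4.1 plans one tabulated blood-pressure display: "A shift table from baseline systolic blood pressure and diastolic blood to worst on-treatment results will be presented". It continues: "The normal/abnormal classification will be made using the criteria defined in table below". Table 2 then gives the limits, and meeting any one of them is enough. For systolic pressure (SBP) they are "value < 80 mmHg value > 129 mmHg"; for diastolic pressure (DBP), "value < 60 mmHg value > 80 mmHg". After that only listings follow: "Vital signs data and clinically relevant abnormalities in vital signs will also be listed".

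Three other places bear on this:

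- SAP 4.12.3 keeps direction in the laboratory shift tables: "Low and/or High abnormal direction will be considered for each parameter".
- SAP 4.2.2 has a rule for several visits falling in one window: "For Shift table, we will consider either Minimum or Maximum available value depending on the direction".
- Protocol 9.4.3.3 plans to identify vital signs above or below range and to summarise them with descriptive statistics. SAP 4.12.4.1 does not carry those statistics forward. The readable items of SAP 4.16 do not list this as a change, although one item there is redacted.

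**The concern.** A two-sided class has no natural 'worst'. If a patient's DBP readings include 55 and 90, the SAP does not say which one enters the table. If 'worst' means the maximum, lows are missed. If it means any reading outside the limits, lows and highs share a cell. On that second reading, a patient who goes from DBP 85 to 50 is abnormal at baseline and abnormal on treatment, so the table records no shift.

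A fall in pressure is a plausible direction to look for here. Protocol 2.3.1.2 and 4.4.1.1 describe vomiting, diarrhoea, decreased appetite and colitis with RXC004, all of which can reduce fluid volume. A reader who took a blood-pressure safety statement from this table could miss such a fall or read it as reassurance.

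**Working it through.** **Inputs from the documents.** The limits are those of Table 2. Baseline is the last assessment before first dose (SAP 4.2.3), taken here as one reading. A patient is counted as abnormal on treatment if any reading is outside the limits.

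**Assumed inputs.** The documents give no blood-pressure means or SDs and no expected number of readings, so there is no plan figure to reproduce.

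- On-treatment readings *k*: 4 (about 7 weeks, the median Phase 1 exposure in protocol 4.4.1.6), 6, and 10 (about 24 weeks).
- DBP mean / between-patient SD / within-patient SD: 70/8/6, 73/8/6, 75/8/6, 78/8/7.
- SBP: 115/12/8, 120/12/8, 125/12/8, 125/13/9, 130/14/10.

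**Single-reading check by hand.** The total SD is the root of the summed variances.

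- DBP 73/8/6: √(64+36) = 10. P(<60) = Φ(−1.3) = 9.7% and P(>80) = 1−Φ(0.7) = 24.2%, together 33.9%. After a 10 mmHg fall the mean is 63: Φ(−0.3) = 38.2% plus 1−Φ(1.7) = 4.5%, together 42.7%. Lows rise roughly fourfold; the pooled figure moves by 9 points.
- SBP 125/13/9: √(169+81) = 15.8. P(<80) = Φ(−2.85) = 0.2% and P(>129) = 1−Φ(0.25) = 40.0%, together 40.2%. After a 10 mmHg fall the mean is 115: 1.3% plus 18.8%, together 20.1%. Lows rise and the pooled figure halves.

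**Worst of *k* readings.** Let p(μ) = Φ((U−μ)/s) − Φ((L−μ)/s) for a patient with true mean μ ~ N(m, b²), where b and s are the between- and within-patient SDs. Then P(abnormal) = 1 − E[p(μ)^k]. Among patients normal at baseline it is 1 − E[p(μ)·p(μ+d)^k] / E[p(μ)], where d is the true change. Numerical integration and simulation agree.

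With no drug effect and *k* from 4 to 10:

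- DBP: 66-95% of all patients are abnormal at worst, and 58-93% of those normal at baseline.
- SBP: 35-87% and 26-75%. At mean 115 the all-patient share is 35-49%; at 125/12/8 it is 63-75%.

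With a true change of 10 mmHg and *k* = 6:

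| Measure | No change | Fall of 10 | Rise of 10 |
|---|---|---|---|
| DBP 73/8/6, pooled, all patients | 77% | 82% | 92% |
| DBP 73/8/6, pooled, normal at baseline | 71% | 85% | 92% |
| DBP 73/8/6, any reading <60, all patients | 27% | 70% | – |
| SBP 125/13/9, pooled, all patients | 71% | 48% | 89% |
| SBP 125/13/9, pooled, normal at baseline | 54% | 29% | 82% |
| SBP 125/13/9, any reading <80, all patients | 1% | 5% | – |

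**Sensitivity for DBP.** At mean 75, *k* = 6, a 10 mmHg fall leaves the all-patient share at about 80%, because 75 and 65 lie equally far from the middle of the 60-80 band; the baseline-normal share goes from 72% to 82%. Masking is weaker at mean 70, *k* = 4: 66% to 81% of all patients, 58% to 82% of those normal at baseline. A 5 mmHg fall moves the baseline-normal share by between −5 and +8 points across the scenarios.

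**Sensitivity for SBP.** The limits are asymmetric: from a mean of 125 the upper limit is 4 mmHg away and the lower limit 45. A fall therefore empties the high side long before it fills the low side. With 125/12/8 and *k* = 6 the pooled share goes from 68% to 41% after a 10 mmHg fall and to 27% after 20 mmHg. At mean 115 a 20 mmHg fall leaves it almost unchanged (41% to 39%).

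**The case against.** The strongest reply is that this is one descriptive table in an open-label Phase II study with no comparison or decision rule attached, and that a fall could be seen elsewhere. Listings show every reading. Protocol 8.3.5 makes clinically relevant deterioration in vital signs reportable as an adverse event, and SAP 4.12.1 tabulates such events by preferred term and grade, which separates hypotension from hypertension. This stands, and it limits the consequence. It does not repair the table, and the descriptive statistics that would show a shift in the mean are in the protocol but not in SAP 4.12.4.1.

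A second reply is that SAP 4.2.2 already makes shift tables directional. It does show that intent. But the rule is written for repeat visits within a window, and SAP 4.12.4.1 names no direction to which it could be applied.

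A reader might also infer more than the documents support:

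- *Most patients become abnormal on an inert drug.* This held for DBP in every scenario tried. For SBP it depends on the assumed mean and number of readings.
- *A real fall barely changes the result.* This is wrong for SBP, where the share usually drops. For DBP the baseline-normal row, from which a shift table is mainly read, does move (71% to 85%).
- *The table is uninformative in both directions.* It is not: a 10 mmHg rise is visible for both pressures.
- *The high limits should be replaced by CTCAE bands.* The SAP applies CTCAE to adverse events and laboratory tests, not vital signs, and gives no blood-pressure bands, so nothing in the documents requires this.

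**Conclusion.** The point holds as a fault of definition. Direction and 'worst' are unspecified for blood pressure, although the SAP handles both for laboratory data. That conclusion follows from the text and needs no simulation. The size rests entirely on assumed distributions and numbers of readings. Under them, a 5-10 mmHg fall in DBP is partly or largely masked, and a 10 mmHg fall in SBP lowers the abnormal share and so looks like improvement. Because rises remain visible and individual events are captured elsewhere, the fault is minor and confined to this table.

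**What to change.** In SAP 4.12.4.1:

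1. Classify SBP and DBP as Low, Normal or High, keeping the Table 2 limits.
2. Replace the single shift table with two for each pressure: baseline to worst low, using the on-treatment minimum, and baseline to worst high, using the maximum. This matches SAP 4.12.3 and the intent of 4.2.2.
3. Add descriptive statistics by visit, with change from baseline. Protocol 9.4.3.3 already promises descriptive statistics; the by-visit layout follows what SAP 4.12.3 does for laboratory values.

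The cost is SAP wording and one or two extra tables. No new data are needed.
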